3.4.2. Methods to Minimize Bias

To minimize bias, the following measures will be taken:

- Investigational product assignment (KPI-121 1% ophthalmic suspension or prednisolone acetate ophthalmic suspension 1%) will be randomized and masked to the sponsor, subjects, and investigative staff with the exception of a dedicated dosing coordinator. The dedicated dosing coordinator will manage drug dispensing and return, parent/caregiver instruction and initial dosing and will review the dosing diary. Since the KPI-121 1% ophthalmic suspension is only dosed BID, it will be supplemented with BID dosing of vehicle to support the masking.
- The randomization schedule will be generated by the randomization statistician (who is not on the project team) or designee and maintained via the electronic data capture system (EDC) used for the trial.

4. SELECTION OF SUBJECTS**4.1. SUBJECT INCLUSION CRITERIA**

At Visit 1, individuals of either gender and any race will be eligible for study participation if they:

1. Have informed consent and Health Insurance Portability and Accountability Act (HIPAA) authorization provided by a parent or guardian prior to any study-related procedures.
2. Are 0-3 years of age (have not had their 4th birthday) as of the date of surgery.
3. Are candidates for routine, uncomplicated, cataract surgery
 - a. With or without capsulotomy and vitrectomy
 - b. With or without posterior chamber intraocular lens (IOL) implantation
 - c. But not combined with any other surgery.
4. Have a unilateral cataract or have bilateral cataracts and are candidates for surgery:
 - a. On the first eye, and surgery on the second eye is not planned until after the subject completes participation in the study OR
 - b. On the second eye, and surgery on the first eye was uncomplicated, any post-operative inflammation has resolved and anterior chamber cell and flare grades both = 0.

4.2. SUBJECT EXCLUSION CRITERIA

In order for subjects to be eligible at Visit 1 they may not:

1. Have a post-traumatic cataract.
2. Have suspected permanent low vision or blindness in the fellow non-study eye.
3. Have active uveitis in either eye.
4. Have an ocular neoplasm in either eye.
5. Have the presence of any active or suspected viral, bacterial, or fungal disease in either eye.
6. Have a history of glaucoma, ocular hypertension, steroid-induced IOP rise or have an IOP >21 mmHg in either eye at the screening or randomization visit(s).
7. Require the use of any topical ophthalmic medication in the study eye within 2 days prior to surgery and for the duration of the study, except for

- drops that are needed to examine the eye or to prepare for and undergo surgery as well as post-operative antibiotic drops. **NOTE:** Besifloxacin Ophthalmic Suspension is not permitted within 2 days prior to surgery or for the duration of the study.
8. Require the use of systemic or ocular non-steroidal anti-inflammatory drugs within 2 days prior to surgery and for the duration of the study.
 9. Require treatment with systemic, inhaled or ocular corticosteroids within 14 days prior to surgery and for the duration of the study with the exception of intraoperative ocular corticosteroids.
 10. Require a change in use of nutraceuticals or multivitamins within 2 days prior to surgery and for the duration of the study.
 11. Have known hypersensitivity or contraindication to the investigational product(s) or their components.
 12. Have a diagnosis of:
 - a. Severe/serious ocular condition that in the judgment of the Investigator could confound study assessments or limit compliance.
 - b. Severe/serious systemic disease or uncontrolled medical condition that in the judgment of the Investigator could confound study assessments or limit compliance.
 13. Have been exposed to an investigational product within 30 days prior to surgery.

4.3. RANDOMIZATION CRITERIA

To qualify for randomization at Visit 2 (1st post-surgery assessment which may be later on the day of surgery or the following day), a subject must:

1. Have undergone routine, uncomplicated, cataract surgery, with or without capsulotomy and/or anterior vitrectomy and with or without posterior chamber IOL implantation and not combined with any other surgery.
2. Continue to meet inclusion/exclusion criteria with respect to current ocular and medical conditions and medications.
3. Continue to have IOP \leq 21 mmHg in both eyes.

5. PROCEDURES

Written informed consent and HIPAA authorization will be obtained from each subject's parent/guardian prior to any study procedures being performed.

5.1. VISIT DESCRIPTIONS**5.1.1. Visit 1: Screening Visit (Day -14 to Day -1)**

The screening visit will occur no more than 14 days and no less than one (1) day prior to Surgery. After obtaining written informed consent and HIPAA authorization, site staff will perform/assess the following in the order suggested below:

- Assign each screened subject a Subject Identification (ID) number consisting of a three-digit Investigator number plus a four-digit number starting with number 1001. The Subject ID will be used as the primary subject identifier for the duration of the study.
- Collect the following information and perform the following assessments (when obtainable) (**NOTE:** All ocular assessments must be performed in both eyes):
 - Non-ocular and ocular medical history
 - Medications taken during the 30 days prior to screening and concomitant medication usage
 - Visual acuity (Snellen, Optotype recognition, Central/Steady/Maintained with Fix and Follow or Fix and Follow alone per the subject's age and as determined by the Investigator and used for all study visits for the subject)
 - Signs of anterior ocular inflammation – cell and flare grading, corneal clarity, conjunctival injection, chemosis, hypopyon as well as vitritis and wound integrity (Slit lamp biomicroscopy, ophthalmoscopy or light examination depending on subject's tolerance. The method used for these assessments will be determined by Investigator and used for all study visits for the subject)
 - Symptoms of anterior ocular inflammation - photophobia and lacrimation
 - IOP measurement
 - Dilated Ophthalmoscopy
 - Inclusion/exclusion criteria evaluation
- Ensure subjects to return for surgery in no more than 14 days.

5.1.2. Surgery**Pre-surgical Procedures:**

Cataract surgery will occur no more than 14 days and no less than 1 day after Visit 1 and the following will be performed:

- Routine pre-surgical care and procedures as determined by the Investigator

Surgical Procedure

The surgeon will perform his or her routine cataract surgical procedures.

Post-Surgical Procedures

- Routine post-surgical care and instructions will be provided by the Investigator.
- Medications routinely administered prior to, during and immediately following cataract surgery will be collected as a summary document and included as a source document but not listed in the EDC. Only non-routine medications will be collected as concomitant medications in the subject's source document and eCRF.

5.1.3. Visit 2: First Post-Operative Assessment Visit (This may be later on the day of surgery or the following day. This will be considered Day 1)

The following assessments/evaluations will be performed (**NOTE:** All ocular assessments must be performed in both eyes):

- Review use of any concomitant medications since Visit 1
- Assess occurrence of any additional medical or ophthalmic history since Visit 1
- Perform (when obtainable):
 - Visual acuity assessed using the same method used at the screening visit
 - Signs of anterior ocular inflammation – cell and flare grading, corneal clarity, conjunctival injection, chemosis, hypopyon as well as vitritis and wound integrity assessed using the same method used at the screening visit

- Symptom assessment of anterior ocular inflammation – photophobia and lacrimation
- IOP measurement
- Subjects whose surgery is confirmed to have been routine and who continue to meet inclusion/exclusion criteria with respect to current ocular and medical conditions and medications, including having intraocular pressures ≤ 21 mmHg in both eyes, will be randomized to receive either KPI-121 1% ophthalmic suspension dosed BID AND vehicle dosed BID or prednisolone acetate ophthalmic suspension 1% dosed QID.
- Randomization will be performed through the EDC system.

Initiation of Dosing

- Dispense the investigational product kit according to the randomization results.
- The dedicated dosing coordinator will review the investigational product kit, bottles, dosing times and proper method for instillation including but not limited to shaking investigational product bottle prior to each instillation with the parent/guardian and provide written instructions.
- Provide the Dosing Diary and review instructions for completion.
- The parent/guardian will administer the first dose of double-masked investigational product, in the study eye in the clinic under the supervision of a designated dosing coordinator.
- Study staff will assess the occurrence of any AEs after investigational product administration. **NOTE:** Signs and symptoms of inflammation typically seen after uncomplicated, cataract surgery will not be classified as AEs, but rather the condition under study.
- Schedule the subject to return to the clinic on Day 8 ± 2 days for Visit 3.
- Ask parent/guardian to bring the Dosing Diary with them to the next clinic visit.

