6.2. CONCOMITANT MEDICATIONS

With the exception of peri-operative standard of care medications, all medication that the subject has taken 30 days prior to Visit 1 and through Visit 6 or discontinuation from the study will be recorded in the subject's chart/source documents and the eCRF. The name of the drug, dose, route of administration, duration of treatment (including start and stop dates), frequency, indication, and whether or not the medication was taken due to an AE will be recorded for each medication.

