6.2.1. Permitted Medications

Medications not specifically excluded in [Section 6.2.2](#) may be taken as necessary. Concomitant treatment with ocular antibiotics at the discretion of the Investigator is allowed (with the exception of besifloxacin). Medications routinely administered (and not explicitly prohibited in this protocol) as part of an uncomplicated cataract surgery

procedure are allowed. These medications will be collected in a summary source document and will not be captured within the eCRF. If there is a change from the standard of care as documented in the source document, the medication will be added to the eCRF. Further, the routine medications administered as part of routine cataract surgery are not expected to be associated with treatment for AEs unless otherwise indicated. **NOTE:** Any medication administered as part of the routine surgery that is ongoing subsequent to the surgical procedure should be captured in the eCRF as a concomitant medication.

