6.2.2. Medications Not Permitted

Use of the following medications is not allowed during the study and for the timeframes specified:

Within 30 days prior to surgery and for the duration of the study:

- Other investigational products.

Within 14 days prior to surgery and for the duration of the study:

- The use of systemic, inhaled or ocular corticosteroids with the exception of intraoperative ocular corticosteroids.

Within 2 days prior to surgery and for the duration of the study:

- The use of any topical ophthalmic medication in the study eye, except for drops that are needed to examine the eye or to prepare for and undergo surgery, including post-operative antibiotic drops. **NOTE:** besifloxacin ophthalmic suspension is not permitted.
- The use of systemic or ocular non-steroidal anti-inflammatory drugs.
- Change in use of nutraceuticals or multivitamins.

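### Does keeping routine intraoperative ocular corticosteroid out of the eCRF weaken the comparison of the two arms?

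*Combined protocol and SAP*

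**What the plan says.** Exclusion criterion 9 (Section 4.2) bars systemic, inhaled and ocular corticosteroids from 14 days before surgery and "for the duration of the study with the exception of intraoperative ocular corticosteroids". Section 6.2.2 repeats the exception: "The use of systemic, inhaled or ocular corticosteroids with the exception of intraoperative ocular corticosteroids". Technique is left to the operator (Section 5.1.2): "The surgeon will perform his or her routine cataract surgical procedures".

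Three sections agree on recording.

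- Section 5.1.2: routine peri-surgical medications "will be collected as a summary document and included as a source document but not listed in the EDC", and "Only non-routine medications will be collected as concomitant medications in the subject's source document and eCRF".
- Section 6.2: the general medication record opens "With the exception of peri-operative standard of care medications, all medication that the subject has taken 30 days prior to Visit 1".
- Section 6.2.1, on routine surgical drugs: "These medications will be collected in a summary source document and will not be captured within the eCRF". It adds two routes into the eCRF. One is for departures: "If there is a change from the standard of care as documented in the source document, the medication will be added to the eCRF". The other is for routine drugs that continue after the operation.

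Section 9.1.1 summarizes background variables by study group without naming this one. Sections 9.1.2 and 9.3 limit the analysis to descriptive statistics.

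**The concern.** Both arms receive a topical corticosteroid, and the outcomes of most interest, Day 15 anterior chamber cell grade and IOP, are ones that a further ocular steroid could plausibly affect. The recording rule logs the unusual and leaves out the habitual. A surgeon who always gives a steroid leaves a blank in the eCRF, while one who gives it once, off routine, leaves an entry. A blank can thus mean no steroid or the usual steroid, and a table built from the eCRF alone could mislead.

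With about 60 children at about 20 centres, and no stratification described, the arms could differ in exposure without the database showing it. If that mattered, a difference in Day 15 success or in IOP might be credited to the study products when part of it came from the operating room. A natural response would be a per-child eCRF item for Surgery day, tabulated by arm.

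**Working it through.** **Plan's own figure.** Section 9.2 asks for 30 per group to give at least a 95% chance of seeing an AE of 10% incidence. The formula is 1 − (1 − 0.10)^n. It gives 0.9477 at n = 28, 0.9529 at n = 29 and 0.9576 at n = 30, so the stated size holds. Nothing in it depends on intraoperative steroid.

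**Timing.** Sections 3.4, 5.1.2 and 5.1.3 give the order: surgery, then Visit 2 (later that day or the next), then randomization, then the first dose. The exposure is fixed before allocation. It is a baseline factor, and treatment cannot cause an imbalance in it.

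**Chance of imbalance.** Inputs: 60 eyes, 30 per arm (Section 3.4, Figure 1; Section 9.2). The documents give no exposure rate, so the number exposed, K, is varied. With unrestricted 30/30 allocation, the number a exposed in one arm has probability C(K, a) × C(60 − K, 30 − a) / C(60, 30). A gap of 20 points or more means |a − (K − a)| ≥ 6 eyes.

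| Exposed of 60 | Chance of a gap of 20 points or more |
|---|---|
| 3 or 57 | 0% |
| 6 or 54 | 2.4% |
| 15 or 45 | 7.2% |
| 18 or 42 | 15.8% |
| 24 or 36 | 18.7% |
| 30 | 19.6% |

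Odd K needs a gap of 7 eyes, so the chance is lower: 9.5% at 19 or 41, 10.3% at 21 or 39, and 12.0% at 29 or 31. The maximum over all K is 19.6%.

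**Effect of restricted allocation.** The documents describe neither blocking nor stratification, and they do not exclude them. As an illustration, assume 20 sites of 3 children, each site split 2:1 or 1:2 at random, with all-or-none steroid use by site. Each exposed site then contributes +1 or −1 eye to the gap.

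- Ten exposed sites (50% use): 2 × (1 + 10 + 45)/1024 = 10.9%.
- Six exposed sites (30% use): 2/64 = 3.1%.

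**Shift in the result.** Shift = imbalance × steroid effect. For a 20-point imbalance and an assumed effect of 10 to 40 points on Day 15 success, this is 0.20 × 0.10 = 2 points to 0.20 × 0.40 = 8 points.

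**Comparison with sampling error.** At an assumed 60% success, the standard error of the arm difference is √(2 × 0.6 × 0.4 / 30) = 12.65 points. The largest shift above is 8/12.65 = 0.63 of one standard error. Simulation with 30%, 50% or 70% exposed and an effect of 10, 20 or 40 points (200,000 runs per setting, overall success 60%) gave a standard deviation of the arm difference of 12.63 to 12.69 points. The usual formula therefore already contains this source of variation.

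**Cost of recording it.** Yes/no, drug, route and amount make four fields: 4 × 60 = 240 data points, at about 60/20 = 3 children per centre. It would also need an EDC change and a further protocol amendment (three are already listed), with IRB approval before implementation under Section 12.1.

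**The case for a change.** The strongest opposing argument is that a purely descriptive trial rests on its background tables, because no model or test stands behind the comparison. A steroid trial should be able to say how much other steroid its patients had. The substitutes are imperfect. Visit 2 signs are graded only when obtainable. Visit 2 IOP is required (Appendix 4), but randomized children are limited to 21 mmHg or below, and neither measure shows whether a steroid was given. Section 5.1.2 does not say whether the summary document is kept per site or per child. If it is per site, it shows the surgeon's custom, and a usual steroid omitted in one child might go unlogged.

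Most of this stands as description. Balance cannot be read directly from the database, and an eCRF-only table would be incomplete. It does not follow that the plan must change. The proposed item would feed no test, no adjusted estimate and no outcome display by exposure; it would add a few baseline rows and perhaps a sentence. Much of that can be had from what the plan already keeps: the summary source document, the departures sent to the eCRF, and the investigator number built into the Subject ID (Section 5.1.1), which links each child to a surgeon's routine. Visit 2 signs and IOP also describe the eye before the first study dose in both arms.

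**Conclusion.** No change to the plan. The gap is genuine but changes no planned result: a sponsor who follows the protocol as written gets the same valid descriptive comparison with or without the extra field. An imbalance of 20 points or more is absent in at least four trials in five under unrestricted 30/30 allocation, and less likely still in the site-balanced illustration. If one did occur, it would move the Day 15 arm difference by 2 to 8 points, at most about two-thirds of a standard error that already allows for it. These figures rest on assumed exposure rates, an assumed steroid effect of 10 to 40 points and an assumed 60% success; the documents give none of them. The shift was worked out for Day 15 success only. For IOP the argument from timing is the same, but no figure can be given. Leaving routine surgical drugs in source documents is a fair trade of detail against workload, and authors who want the context can take it from there for the study report.

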5.1.4. Visit 3: Study Visit (Day 8 ± 2 days)

The following assessments/evaluations will be performed (**NOTE:** All ocular assessments must be performed in both eyes):

- Review use of any concomitant medications since the last visit
- Assess occurrence of any AEs since the last visit
- Perform (when obtainable):

- Visual acuity assessed using the same method used at the screening visit
- Signs of anterior ocular inflammation – cell and flare grading, corneal clarity, conjunctival injection, chemosis, hypopyon as well as vitritis and wound integrity assessed using the same method used at the screening visit
- Symptom assessment of anterior ocular inflammation – photophobia and lacrimation
- IOP measurement
- Modified Global Overall Assessment of Postoperative Inflammation
- Review dosing compliance/Dosing Diary.
- Instruct parents/caregivers to continue investigational product and return for Visit 4 on Day 15 ± 2 days. Remind them to bring the investigational product kit and Daily Dosing Diary with them.

5.1.5. Visit 4: Study Visit (Day 15 ± 2 days)

The following assessments/evaluations will be performed (**NOTE:** All ocular assessments must be performed in both eyes):

- Review use of any concomitant medications since the last visit
- Assess occurrence of any AEs since the last visit
- Perform (when obtainable):
 - Visual acuity assessed using the same method used at the screening visit
 - Signs of anterior ocular inflammation – cell and flare grading, corneal clarity, conjunctival injection, chemosis, hypopyon as well as and vitritis and wound integrity assessed using the same method used at the screening visit
 - Symptom assessment of anterior ocular inflammation – photophobia and lacrimation
 - IOP measurement
 - Modified Global Overall Assessment of Postoperative Inflammation
- Review dosing compliance/Dosing Diary.
- Collect initial investigational product Kit and dispense second Kit.
- Instruct parents/caregivers to return for Visit 5 on Day 29 ± 2 days. Remind them to bring the investigational product Kit and Dosing Diary with them.

5.1.6. Mid-Visit Phone Contact (Day 21 - 23)

A phone contact will be made between Visits 4 and 5 (Day 21 -23) to assess subject progress, including but not limited to: continued dosing, adverse events, parent/caregiver questions, concerns and comments.

5.1.7. Visit 5: End of Investigational Product Use (Day 29 ± 2 days)

The following assessments/evaluations will be performed (**NOTE:** All ocular assessments must be performed in both eyes):

- Review use of any concomitant medications since the last visit
- Assess occurrence of any AEs since the last visit
- Collect investigational product Kit
- Collect diary
- Perform (when obtainable):
 - Visual acuity assessed using the same method used at the screening visit
 - Signs of anterior ocular inflammation – cell and flare grading, corneal clarity, conjunctival injection, chemosis, hypopyon as well as and vitritis and wound integrity assessed using the same method used at the screening visit
 - Symptoms of anterior ocular inflammation - photophobia and lacrimation
 - IOP measurement
 - Dilated ophthalmoscopy
 - Modified Global Overall Assessment of Postoperative Inflammation

Completion of investigational product at Visit 5 may be followed by treatment or taper using a commercially available product as determined by the Investigator. Regardless of treatment and after cessation of investigational product, parents/caregivers will be instructed to return for follow-up on Day 36 ± 2 days for Visit 6.

5.1.8. Visit 6: Follow-Up Visit (Day 36 ± 2 days)

The following assessments/evaluations will be performed (**NOTE:** All ocular assessments must be performed in both eyes):

- Use of any concomitant medications since the last visit
- Occurrence of any AEs since the last visit
- Perform (when obtainable):
 - Visual acuity assessed using the same method used at the screening visit
 - Signs of anterior ocular inflammation – cell and flare grading, corneal clarity, conjunctival injection, chemosis, hypopyon as well as vitritis and wound integrity assessed using the same method as used at the screening visit
 - Symptom assessment of anterior ocular inflammation - photophobia and lacrimation
 - IOP measurement
 - Modified Global Overall Assessment of Postoperative Inflammation

